## 9.3 POPULATIONS FOR ANALYSES

- Specific Aim 1, Primary Endpoint  
Intention-to-Treat (ITT) Analysis Population: Randomized family members of critically ill patients

- Specific Aim 2, Secondary Endpoint  
ITT Analysis Population: Randomized patients experiencing hospitalization due to critical illness
- Specific Aim 3, Other Outcomes  
Analysis Population: Participating family members and clinicians, administrators

## 9.4 STATISTICAL ANALYSES

### 9.4.1 GENERAL APPROACH

Our primary analysis approach involves mixed effects models. This likelihood-based approach assumes that missing data (responses) are missing at random. However, this assumption may not hold, so further sensitivity analysis is necessary. Multiple imputation using MICE will be performed to address missing data. Missing values will be imputed based on patient characteristics (minority race, age and having three or more chronic diagnoses), family characteristics (age, education, employment, self-reported health status and financial situation) and outcomes from previous time points. Twenty imputations will be performed, and final results will be pooled. The multiple imputation approach will be useful for our sensitivity analyses which include adjustment for covariates, some of which may be missing for some participants.

We will also perform sensitivity analyses regarding handling of missing data and enrollment characteristics of participants. We will consider different approaches and summarize any similarities and differences in results or conclusions from these approaches.

Our goal will be to minimize missing data through minimizing respondent burden, offering multiple methods for survey completion, and having trained staff with repeated contact with participants. However, data could still be missing due to skipping individual items on a survey, omissions in EHR, lack of follow-up, or death. We will quantify the amount of missing data, evaluate associations with participant characteristics, and minimize bias by applying appropriate methods to account for missing data.

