## 9.2 SAMPLE SIZE DETERMINATION

The primary focus for sample size estimation is the primary outcome: mean family member depression over 6 months as assessed by the HADS depression subscale. For all calculations, we assume a two-sided test with a significance level of 0.05. If we assume 300 total family members (1 family member per patient and 150 per arm), a standard deviation of HADS depression scores of 4.2 points in both arms, 3 measurements of depression (at 1,3, and 6 months), and an intraclass correlation (ICC) of 0.2, we will be able to detect a difference in mean depression of at least 0.93 points with 80% power and 1.07 points with 90% power (Power Table Below). These detectable differences at 80% power become 0.86 if the ICC is 0.1 and 1.05 if the ICC is as high as 0.4. If we had only 1 measurement instead of 3 per family member or, equivalently, if the ICC were 1, we would have 80% power to detect a difference of at least 1.36 points. Across all of these varying conditions, detectable differences are slightly within or below estimates of the minimally clinically important difference (MCID) of 1.6 to 2.0 available from the literature, suggesting we will have adequate power to identify a minimally clinically important difference. Although these MCIDs and minimum detectable effects are just estimates, they provide the best available evidence that power will be adequate to detect relatively small but important differences. We anticipate >80% complete data for all outcomes so we will randomize 376 patients to achieve 300 patients and at least 300 family members with complete data. If our response rate is 70%, then we would expect responses for 263 patients and at least 263 family members and with an ICC of 0.2, we would be able to detect a difference in mean depression of at least 0.99 points with 80% power. If we have more than 1 family member per patient (1.5 is expected), we will be able to detect smaller differences at the same power. In addition, we have 80-90% power to detect reasonable effects for other continuous outcomes in Aim 1. For the binary outcome of goal-concordance care, we have about 80% power to detect a difference in proportion concordant of 0.6 and 0.7, with 3 measurements from each of 300 total participants and an ICC of 0.13; the estimate of 0.6 for the controls is from a prior study and our preliminary data. We targeted power to identify differences within or slightly less than available estimates of “minimally important clinical differences” so that we would be confident that we would be powered to detect a minimally important clinical difference.

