### 9.4.2 ANALYSIS OF THE PRIMARY ENDPOINT(S)

- Specific Aim 1, Primary Endpoint

Our primary outcome is family member symptoms of depression over the 6-months post-randomization period. We will follow the intention-to-treat principle. Our primary analysis will use a linear mixed effects model with family member symptoms at all time points (1,3,6 months) as the response, main effects for intervention and time points, and a random effect to account for multiple measurements (time points) per family member. Given multiple family members per patient, we will also include a random effect for family. Time point is included as a factor variable to allow for nonlinear effects. We will also adjust for site, since randomization is stratified by site, and consider adjustment for response (symptoms of depression for primary outcome) at baseline (randomization). This model allows the average response to be different at 1, 3, and 6 months, but assumes the intervention has the same effect at each of these times. The secondary analysis allows the effect of intervention to be different across time by including an interaction between time and intervention. The advantage of using the data at all three time points and

a mixed model approach is that we can gain precision; it also allows for missing responses, assuming the responses are missing at random. We will use a similar approach for the other continuous family and patient outcomes, and a generalized linear mixed effects model for the binary outcome of goal-concordant care. As a sensitivity analysis, we will consider models including only one family member per patient, chosen randomly.

---

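### The multiple-imputation predictor list in section 9.4.1 omits randomised arm; followed as written, it biases that sensitivity analysis toward no effect, with a minor consequence

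*Combined protocol and SAP*

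**What the plan says.** Section 9.4.1 makes a likelihood-based mixed model the primary approach and notes that it relies on data being missing at random. It continues: "However, this assumption may not hold, so further sensitivity analysis is necessary. Multiple imputation using MICE will be performed to address missing data". It then gives the predictors: "Missing values will be imputed based on patient characteristics (minority race, age and having three or more chronic diagnoses), family characteristics" (age, education, employment, self-rated health and financial situation) "and outcomes from previous time points". Twenty imputations are to be pooled. The section also gives missing covariates as a use for imputation, and adds: "We will also perform sensitivity analyses regarding handling of missing data and enrollment characteristics of participants".

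Section 9.4.2 defines the analysis model. It has "main effects for intervention and time points", random effects for family member and family, and adjustment for site. Of the mixed model it says "it also allows for missing responses, assuming the responses are missing at random". Neither section, nor any other, puts randomised arm into the imputation model.

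On the amount of missing data, section 9.2 expects more than 80% complete data and also considers a worse case: "If our response rate is 70%, then we would expect responses for 263 patients and at least 263 family members".

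**The concern.** An imputation model should contain the terms of the analysis model that will be fitted to the completed data, above all the term being tested. If arm is left out, missing scores in both arms are drawn from one pooled regression. An imputed score then carries the arm effect only as far as it shows in that person's earlier observed follow-up scores. A person with no follow-up carries none of it, because the baseline score precedes randomisation.

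The result is bias toward zero in the analysis meant to test the primary result against missing data. The imputed estimate would differ from the mixed-model estimate because of how it was built. A real benefit could look fragile, and a real harm would be understated.

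**Working it through.** **Inputs from section 9.2.** SD 4.2; three follow-up measurements; ICC 0.2 (range 0.1 to 0.4); two-sided 0.05; 376 patients randomised; response 80% or 70%, so 20% or 30% missing; smallest important difference 1.6 to 2.0 points. The plan states no figure for imputation bias.

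**The plan's own figures.** The SD of a three-wave mean is 4.2 × √[(1 + 2 × 0.2)/3] = 2.869. With 150 per arm the detectable difference at 80% power is (1.960 + 0.842) × 2.869 × √(2/150) = 0.93, as stated. With 376 × 0.70 = 263 people, or 131.5 per arm, it is 0.99, as stated.

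**Assumptions for the bias.** Outcomes missing completely at random, equal correlation ρ (the ICC) between all waves including baseline, a constant arm effect, and imputation from baseline and earlier waves without arm. Under equal correlation, the regression weight on each earlier score is ρ/(1+ρ) for month 3 and ρ/(1+2ρ) for month 6. At ρ = 0.2 these are 0.167 and 0.143.

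**Reading 1: a fraction m is missing at every wave.**
- Nobody in m returns any follow-up: the retained share of the effect is 1 − m. The loss is 20% or 30% at any ICC.
- Each wave is missing independently, ρ = 0.2, m = 0.20:
  - month 1: 0.800
  - month 3: 0.800 + 0.20 × 0.167 × 0.800 = 0.827
  - month 6: 0.800 + 0.20 × 0.143 × (0.800 + 0.827) = 0.846
  - mean 0.824, a loss of 17.6%
- The same steps at m = 0.30 give 0.700, 0.735 and 0.762, a loss of 26.8%. Over ICC 0.1 to 0.4 the losses are 16.0-18.6% and 24.8-28.2%.

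**Reading 2: 20% or 30% is cumulative dropout by month 6, in equal steps.** At ρ = 0.2 and 20%, one fifteenth (0.0667) drops out before each wave.
- month 1: 1 − 0.0667 = 0.933
- month 3: 0.867 + 0.0667 × 0.167 = 0.878
- month 6: 0.800 + 0.0667 × 0.143 × 1.167 + 0.0667 × 0.143 × 2 = 0.830
- mean 0.880, a loss of 12.0%

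At 30% the loss is 17.9%. Over the ICC range it is 11.1-12.6% and 16.6-18.8%.

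**Reading 3: 20% or 30% of people lack at least one wave, waves missing independently.** The rate per wave is 1 − 0.80^(1/3) = 0.072 or 1 − 0.70^(1/3) = 0.112. The steps of Reading 1 then give losses of 5.5-6.6% and 8.8-10.4%.

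**Simulation check.** Large-sample simulations of the same list agree, within simulation error and the choice of predictors:

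| Meaning of the rate | Loss at 20% | Loss at 30% |
|---|---|---|
| Every wave | about 16-20% | about 24-30% |
| Cumulative by month 6 | about 10-13% | about 15-19% |
| Any wave, independent | about 5-7% | about 9-11% |
| Every wave, arm added to the list | about 0% | about 0% |

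**Consequence at the plan's important difference.** In the worst pattern a true 1.6 becomes 1.6 × 0.80 = 1.28 or 1.6 × 0.70 = 1.12. Both exceed the detectable differences of 0.93 and 0.99. A simulation with 1.5 family members per patient (assumed within-family correlation 0.1, ICC 0.2) found that the listed imputation lost significance in under 1% of trials whose analysis without imputation was significant.

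**The case against.** The strongest reply is that the list is not said to be exhaustive. It may name auxiliary variables that supplement the terms in section 9.4.2, and many analysts would include arm without being told. That is possible, and it is why the point is conditional. But the sentence says what values will be imputed from, with no wording to mark the list as partial, and a pre-specified rule should not need an analyst to depart from it.

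A second reply is that section 9.4.1 gives missing covariates as a use for imputation. However, using outcomes from earlier time points as predictors suggests that outcomes are imputed too.

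A third reply concerns size, and it stands. Section 9.2 speaks of more than 80% complete data, so 20% is an upper bound in the base case, and it need not apply to every wave. The smaller readings above are as consistent with the text as the larger one.

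Three stronger readings are tempting, and the documents do not support them:
- **That the main result is biased.** The primary mixed model contains the intervention term and imputes nothing.
- **That the plan doubts missing at random yet has no answer to it.** The imputation also rests on that assumption, but it uses variables beyond those in the primary model. The section also promises further missing-data sensitivity analyses and undertakes to "minimize bias by applying appropriate methods to account for missing data". Asking for a particular non-random analysis would be a preference.
- **That baseline HADS is missing from the predictors.** Section 4.1 collects HADS in the initial survey, so earlier outcomes already cover it.

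**Conclusion.** Wrong as written, with a minor consequence. The listed predictors, applied literally to missing outcomes, shrink the estimated effect even when the missing-at-random assumption holds. The documents do not settle which missingness pattern applies, so the every-wave figures of 16-20% and 24-30% should not be read as the expected size.

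The figures rest on an equal correlation between waves, a constant effect and data missing completely at random. Two variations lower the every-wave figures: about 15% and 23% at ICC 0.4 if baseline HADS is not used, and about 12-15% and 19-22% for intermittent loss if later waves also serve as predictors (ICC 0.2 to 0.4). The direction of the bias, and its removal once arm is included, did not depend on these choices.

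Only the multiple-imputation sensitivity analysis is affected. The bias is toward no effect, so it would not create a false claim of benefit. At a true 1.6 points it would rarely change the significance conclusion.

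**What to change.** In section 9.4.1, state that randomised arm is in the imputation model, or that imputation is done separately by arm. Add the other analysis-model terms, such as site, and describe the listed characteristics and earlier outcomes as further predictors. Naming arm removes the bias; site is included for consistency with section 9.4.2. The cost is one clause of text and a small programming change. No new data are needed, and the primary model and sample size stay as they are.

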Information & Resources Provision Arm/Comparator: This new study arm is an adaptation to the Facilitator Protocol for use during the COVID-19 pandemic. For those randomized to "Control/Usual Care," participation in this comparator arm will be available at the participant's request. The goal of this comparison group is to offer family members a contact person for questions related to their loved one's care. The resource person (trained study staff) will contact family members within 1-2 days of enrollment and randomization. They will introduce themselves as a resource for finding or providing information in

this stressful and difficult time. All contact will be by telephone or UW HIPAA-compliant Zoom on the following schedule:

- a. Within 1-2 days of randomization
- b. Within 1-2 days of transfer to acute care.
- c. Within 1-2 days of hospital discharge.

The resource person is intended to provide information and help families connect with the right person at the hospital or on the patient's healthcare team to provide help and support.

Intervention Administration: Intervention activities will be conducted with intervention subjects only. During the ICU stay, facilitators will interact in person by telephone or UW HIPAA-compliant Zoom with patients and family subjects, and those clinicians (physicians, nurses, social workers, spiritual care, etc.) involved with patients' care. Following the ICU stay, facilitators will interact with patients, family and clinicians in person and by phone or UW HIPAA-compliant Zoom for 3 months from randomization (when most first readmissions occur) or for 1 month after a patient death occurring in the first 3 months. In-person contacts, when possible, will include visits to patients' homes and/or care facilities; phone or UW HIPAA-compliant Zoom contacts will include calls to patients, families and clinicians. Facilitators will visit with or contact patients and families on the following schedule: daily during the ICU stay, every 72 hours or more frequently on the acute care floor, weekly during the first month following hospital discharge, and twice monthly for the remaining intervention period (3 months from randomization). Facilitators will have the leeway to use their clinical judgment if additional contacts are needed and may extend the follow up period for up to 6 months from randomization if needed. Facilitators will carry a caseload of up to 20 patients per facilitator per month.

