**Intervention Fidelity:** We will record type (mode), frequency and duration of all facilitator contacts for each patient and family so that we will have this information to assess intervention fidelity as well as “dose.” We will also ask participants for permission to periodically audio-record their visits with the interventionist. This procedure will assist in monitoring and maintaining intervention delivery. De-identified transcripts may also be used for training future interventionists.

**Outcome Assessment:** Both intervention and control subjects will be asked to complete questionnaires. At baseline/enrollment, prior to the facilitator’s involvement, both intervention and control group subjects will meet or confer with the research staff who will distribute initial questionnaires. The questionnaires will be self-administered, although study staff will be available to provide assistance. The study staff member collecting the baseline questionnaires will be able to notify the subjects about their randomization status at that time.

Chart abstraction of patient data from EHR will include: age, sex/gender, Race, Ethnicity, primary diagnosis, secondary diagnoses and comorbidities, admission dates (e.g. hospital, ICU, acute care) , discharge dates (e.g. hospital, ICU, acute care), processes of care (e.g. care planning, transitions) , treatment intensity (e.g. receipt of CPR, use of mechanical ventilation), Referrals/Consults (e.g. palliative care) , data required to calculate APACHE II scores (e.g. lab values, Glasgow Coma Scale, medication dosage), outpatient healthcare utilization: number, type and dates of primary and specialty care visits, and date of death. Dates of death will also be collected from publicly available death certificate data.

Family questionnaires will be completed at baseline, 1-month, 3-months, and 6-months post randomization. Questionnaires will contain measures including:

- Relationship Scales Questionnaire (RSQ) – initial survey
- Hospital Anxiety and Depression Scale (HADS) – initial and follow-up surveys

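### The imputation model in 9.4.1 leaves out the patient's death, so it shares the primary model's blind spot and cannot check the missing-at-random assumption where a departure is most foreseeable

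*Combined protocol and SAP*

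**What the plan says.** Section 9.4.1 makes a likelihood-based mixed model the primary approach. It concedes that missing at random may not hold and that sensitivity analysis is therefore needed. The one method it specifies is MICE with 20 imputations. The predictors are three patient characteristics (minority race, age, three or more chronic diagnoses), then "family characteristics (age, education, employment, self-reported health status and financial situation) and outcomes from previous time points". Patient death, later waves, treatment arm and site do not appear.

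The same section says that "data could still be missing due to skipping individual items on a survey, omissions in EHR, lack of follow-up, or death". Section 4.1 provides for dates of death: "Dates of death will also be collected from publicly available death certificate data". Section 7.1 continues chart abstraction after withdrawal unless the subject revokes access.

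Contact after a death differs by arm. In 4.1 the facilitator stays with intervention families for three months from randomization "or for 1 month after a patient death occurring in the first 3 months". For controls, the contact that 8.1 lists at death is a condolence card. In both arms the after-death questionnaire, which includes HADS, replaces the next scheduled form and goes out at least four weeks after the death (4.1).

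The primary model in 9.4.2 has arm, time, site, random effects and possibly baseline HADS-D. It has no death term.

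**The concern.** Death of the patient may well affect both the relative's depression score and the chance that a form comes back. Mortality will not be trivial: 5.1 admits patients with a median survival of about two years or a hospital mortality risk of at least 15%. Section 5.5 presents facilitator contact as a retention strategy, and after a death only one arm has it. A difference between arms in response among the bereaved is therefore foreseeable.

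If it occurs, the arm with better bereaved response has more grieving relatives among its observed scores. Neither the primary model nor the listed imputation can correct for that, because neither sees death. The two analyses would then tend to agree, and the agreement could be taken as support for missing at random when both share the same gap.

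**Working it through.** **1. The plan's own figure.** Section 9.2 says that "we assume a two-sided test with a significance level of 0.05". Its other inputs are 150 relatives in each arm (one for each patient), an SD of 4.2, three follow-up waves and an ICC of 0.2.

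- SE = 4.2 × √[(2/150) × (1 + 2 × 0.2)/3] = 0.331
- Detectable difference at 80% power = (1.960 + 0.842) × 0.331 = 0.93
- At 90% power = (1.960 + 1.282) × 0.331 = 1.07

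Both match 9.2. The yardsticks are therefore 0.93 points and an SE of 0.33.

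**2. Hand calculation of the mechanism.** Let d be the proportion of patients dead by a wave, r_B and r_N the response of bereaved and other relatives, and δ the bereavement effect on HADS-D. The bereaved share among responders in an arm is d·r_B / [d·r_B + (1 − d)·r_N]. If death is ignored, the bias at that wave is about δ times the difference in this share between arms.

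Assumed, because the documents give no values: d = 15/22/30% at 1/3/6 months, r_N = 85%, r_B = 80% (intervention) against 60% (control).

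| Wave | Share, intervention | Share, control | Difference |
|---|---|---|---|
| 1 month | 0.120/0.8425 = 0.142 | 0.090/0.8125 = 0.111 | 0.032 |
| 3 months | 0.176/0.839 = 0.210 | 0.132/0.795 = 0.166 | 0.044 |
| 6 months | 0.240/0.835 = 0.287 | 0.180/0.775 = 0.232 | 0.055 |

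The mean difference is 0.0435. With δ = 2 the bias is 0.09; with δ = 3 it is 0.13, before any correction from earlier scores. If r_B is equal in both arms, the difference and the bias are zero.

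**3. Simulation on the same assumptions.** No true effect, arm in the imputation model, n = 376, 600 trials per setting, ICC 0.2 to 0.4, δ of 2 to 3 points, Monte Carlo SE 0.005. Bias in the four settings:

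- listed predictors: 0.085, 0.081, 0.119, 0.112
- all waves, no death: 0.077, 0.069, 0.107, 0.093
- all waves plus death: 0.002, 0.000, −0.004, −0.005

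**4. Separate simulation.** True effect −1.0, 30% dead by 6 months (20% by month 1), ICC 0.2, δ = 2. Non-bereaved response is 88.6% in the first row and 85% in the others. Entries are bias in HADS-D points; positive is against the intervention. Monte Carlo SE is about 0.01.

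| Bereaved response, intervention/control | Listed + arm | + later waves | + death | + death and later waves | Primary mixed model |
|---|---|---|---|---|---|
| 60/60% | 0.000 | −0.010 | −0.005 | −0.006 | −0.004 |
| 80/60% | 0.089 | 0.089 | 0.002 | −0.001 | 0.079 |
| 85/50% | 0.169 | 0.152 | 0.002 | 0.001 | 0.146 |

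Over δ of 1 to 3, ICC 0.2 to 0.4 and both unequal response patterns, the listed predictors plus arm give 0.03 to 0.25 and the mixed model 0.02 to 0.22. Later waves alone change the bias by at most about 0.04.

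**5. A narrower mechanism.** Confine the 80/60% gap to the first form after a death occurring before the 3-month wave, with other bereaved response 70% in both arms (also assumed). By the formula in step 2:

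- 1 month: difference 0.032, as before.
- 3 months: 7% newly bereaved and 15% bereaved earlier, so r_B is (0.07 × 0.8 + 0.15 × 0.7)/0.22 = 0.732 against (0.07 × 0.6 + 0.15 × 0.7)/0.22 = 0.668. The shares are 0.195 and 0.181, difference 0.014.
- 6 months: zero.

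The mean of 0.015 gives 0.03 (δ = 2) to 0.05 (δ = 3). Simulation of this case gave 0.02 to 0.05.

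**6. Treatment arm.** The near-zero results with death depend on arm being in the imputation model. In the setup of step 4, over the same ranges, death and later waves without arm still leave 0.11 to 0.17 when bereaved response differs. The list read literally, without arm, loses 0.14 to 0.18 of a true 1.0 point even when it does not.

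**The case against.** The strongest reply is that nothing in the documents shows a bias. They give no 6-month mortality, no bereavement effect and no response rate by arm. With equal bereaved response there is no death-related bias, and unequal response does nothing unless bereavement also shifts HADS-D. That stands, so the point can only be conditional.

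The mechanism may also be weak. Continued facilitator contact is tied to deaths in the first three months, the after-death form falls due about when that contact ends, and staff remind both arms. This stands in part and is why the lower end of the range is 0.02. It is not a firm bound, since 4.1 lets facilitators extend follow-up to six months.

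MICE is a sensitivity analysis, and 9.4.1 promises further ones and an examination of what predicts missingness. That limits the seriousness, but no other method is specified.

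A reader might infer three stronger things that the documents and figures do not support:

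- **That restricting predictors to earlier waves causes the bias.** It contributes little. It matters for intermittent gaps, where it mainly discards information.
- **That MICE would depart from the mixed model and so mislead.** The two carry nearly the same bias. The difficulty is that they would agree.
- **That a patient's death removes the HADS outcome.** The after-death questionnaire includes HADS. Death can change response, and the sentence in 9.4.1 naming death covers all data sources, not HADS alone.

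**Conclusion.** The point holds in conditional form. The list omits a variable that is collected independently of questionnaire return, plausibly affects HADS-D, and is followed by different contact in the two arms. If bereavement raises HADS-D by 2 to 3 points and bereaved response is 80% against 60%, the bias is roughly 0.02 to 0.12 points, depending on how widely that response gap applies. That is 2% to 13% of 0.93 and at most about 0.36 of the SE (0.12/0.33). At 85% against 50% with a 3-point effect it reaches about 0.25, or 27% of 0.93. It is zero with equal bereaved response. Its direction is against the intervention if the intervention arm has the better bereaved response, as assumed throughout.

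It would be too strong to say that the imputed analysis is biased, or that imputation is worse than the primary model. The supported conclusion is that MICE as listed cannot serve as the check on missing at random that 9.4.1 calls necessary, because it ignores death just as the primary model does. The sample size is unaffected. This is a change that should be made, not one on which the trial's validity turns.

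**What to change.** In 9.4.1, state that each HADS wave is imputed from treatment arm, site, HADS at baseline and at all other waves, an indicator of patient death before that wave, the covariates already listed, and a term for family clustering.

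The death indicator should be auxiliary: in the imputation model only, not in the analysis model, so that the estimated treatment difference keeps its meaning and is not conditioned on an event after randomization. Arm should be named even if it was always intended, because the correction depends on it.

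The cost is one SAP sentence and slightly more analysis work, with no new data collection. The imputation would still assume missing at random given death and the other predictors. It removes this one foreseeable departure, not every possible one.
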